## Appendix 3 Table 1: Clinical Trials Adverse Event Reporting Table All-Cause Mortality

Population: All Participants Randomized to Stage 1 (N=805); Including All Participants Randomized to Stage 2 (N=683)

	Stage 1	Stage 1 Duloxeti ne	Stage 1 EBEM	Stage 1 ESC	Stage 2 ACT	Stage 2 Duloxeti ne	Stage 2 EBEM	Stage 2 ESC	Stage 2 ACT and Duloxeti ne		Stage 2 ACT and ESC	Stage 2 Duloxeti ne and EBEM	Stage 2 Duloxeti ne and ESC	Stage 2 EBEM and ESC
	(N=xx)	(N=xx)	(N=xx)	(N=xx)	(N=xx)	(N=xx)	(N=xx)	(N=xx)	(N=xx)	(N=xx)	(N=xx)	(N=xx)	(N=xx)	(N=xx)
	Affected /	Affected /	Affected /	Affected /	Affected /	Affected /	Affected /	Affected /	Affected /	Affected /	Affected /	Affected /	Affected /	Affected .
	at Risk	at Risk	at Risk	at Risk	at Risk	at Risk	at Risk	at Risk	at Risk	at Risk	at Risk	at Risk	at Risk	at Risk
	(%)	(%)	(%)	(%)	(%)	(%)	(%)	(%)	(%)	(%)	(%)	(%)	(%)	(%)
Total	x/N (x.x%)	x/N (x.x%)	x/N (x.x%)	x/N (x.x%)	x/N (x.x%)	x/N (x.x%)	x/N (x.x%)	x/N (x.x%)	x/N (x.x%)	x/N (x.x%)	x/N (x.x%)	x/N (x.x%)	x/N (x.x%)	x/N (x.x%)

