At the end of the run-in period, participants will be re-assessed for eligibility. Those meeting requirements for randomization (Section 8) will be randomized to one of the 4 first line treatments. At the baseline visit (Visit 0), all participants will undergo baseline data collection and phenotyping. Data collected for phenotyping will include patient-reported outcomes, spinal imaging, biomechanical assessments, and collection of blood and stool. As described in Section 5.2.2, some of these data will be collected at home prior to the in-person portion of the study visit. A subset of eligible and willing participants (~n=200) will undergo additional phenotyping. Details of the phenotyping assessments are available in Section 9. A subset of phenotypic markers will be re-assessed Week 12 (Visit 1) and Week 24 (Visit 2).

Participants will be assessed for response to treatment Week 12 (Visit 1) and Week 24 (Visit 2) using the PGIC and PEG. Participants will be grouped into one of four responder classes using the PGIC and PEG (see Section 7.1) and assigned to the following based on their responses:

- maintain current treatment (PGIC=1-2, PEG <4),
- augment the current treatment with a randomly selected additional treatment (PGIC=1-2, PEG ≥4),
- be randomized to augmentation or switching to a new treatment (PGIC=3-4), or
- switch to a randomly selected new treatment (PGIC=5-7)

Since the ESC modules focus on self-care, education and a walking program, requiring participants in this intervention arm to cease these activities is not practical; therefore, individuals assigned to ESC at the first randomization will maintain ESC if PGIC is 1-2 and PEG<4 else they will augment ESC with a randomly selected additional treatment. Participants who wish to discontinue treatment but whose

PGIC is less than 6 and who are not contraindicated to their current treatment will be asked to continue first-line treatment until the end of the 12-week treatment period.

All participants will also receive an assessment 4 weeks after the end of the second treatment period for safety purposes (week 28). Participants, whose randomization to the first intervention is at least 36 weeks prior to the end of data collection, will be assessed for outcomes at 36 weeks.

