#### Objectives

The BEST trial was powered for the study's primary objective of estimating an algorithm to assign sequences of two cLBP treatments based on phenotypic markers and an individual patient's response to the initial treatment (i.e., a dynamic treatment regime (DTR)) that optimizes effectiveness, as characterized by the primary and secondary endpoints. In this outcome analysis, we will report the ITT-least squares adjusted mean of the 24-week outcomes of the BEST Trial and associated 95% confidence intervals. It is important to reiterate that the BEST trial was powered for biomarker discovery. This analysis describes the primary and secondary outcomes of the study.

[figure not shown]
In this analysis, we aim to:

- Report on BEST Trial study flow, baseline characteristics, and adverse events
- Estimate 24-week least squares means for study outcomes by Stage 1 treatment assignment.

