#### **Analysis Populations**

The population used for statistical analysis consists of the 805 randomized participants to a Stage 1 treatment.

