## **Analysis**

#### **Analysis Methods**

A linear mixed-effect model (LMM) was used to model the least squares mean of the primary and secondary outcomes at Visit 2 (Week 24) by the Stage 1 treatment assignment for all continuous outcomes. Random intercepts and a linear random slope for time were included to account for subject-level variability. The randomization and minimization algorithm variables are included as

fixed effects. Week indicators as fixed effects were included to model non-linear effects of time. An additional fixed effect was included for the number of treatments a participant was eligible for at the baseline visit. Estimation was conducted using REML and modern optimization approaches with the lme4 package in R. Least squares means were estimated for each Week 24 outcome, along with associated 95% confidence intervals, using the emmeans package in R. Due to the small number of participants on opioids in the BEST Trial sample, we only report counts of participants self-reporting opioid use at Week 24.

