# **Table 1.0. BEST Trial Recruitment Flow Diagram**

# All Randomized Participants at Baseline

Arm/Group Title	Acceptance and Commitment Therapy (ACT) Alone	ACT Plus Duloxetine, Moderate Treatment Response	ACT Plus Evidence Based Exercise and Manual Therapy (EBEM), Moderate Stage 1 Treatment Response	ACT Plus Enhanced Self-Care Therapy (ESC), Moderate Stage 1 Treatment Response	ACT Plus Duloxetine, Low Stage 1 Treatment Response	ACT Plus Evidence Based Exercise and Manual Therapy (EBEM), Low Stage 1 Treatment Response	ACT Plus Enhanced Self-Care Therapy (ESC), Low Stage 1 Treatment Response
Arm/Group Description	This arm included both participants who had a strong response to ACT in Stage 1 and participants who were not assessed for response at the end of Stage 1. In Stage 1, participants randomized to ACT took part in 12 therapy sessions over the course of 12 weeks. Each participant was scheduled for a combination of 4 remote face-to-face visits and 8 therapist-supported online sessions, which included a self-directed module combined with personalized provider coaching delivered via an online messaging system. In Stage 2, strong responders were encouraged to continue to practice ACT skills at home without therapist supervision and were given access to an additional 11 ACT audio modules.	This arm included participants who had a moderate response to ACT in Stage 1 and started Duloxetine in Stage 2 while continuing ACT treatment.	This arm included participants who had a moderate response to ACT in Stage 1 and started EBEM treatment in Stage 2 while continuing ACT.	This arm included participants who had a moderate response to ACT in Stage 1 and started ESC treatment in Stage 2 while continuing ACT.	This arm included participants who had a low response to ACT in Stage 1 and started Duloxetine treatment in Stage 2 while continuing ACT.	This arm included participants who had a low response to ACT in Stage 1 and started EBEM treatment in Stage 2 while continuing ACT.	This arm included participants who had a low response to ACT in Stage 1 and started ESC treatment in Stage 2 while continuing ACT.
Stage 1 Intervention (Weeks 0-12)							
Started							
Completed							
Not Completed							
Reason Not Completed							
Stage 2 Screening (Week 12 Pre- Randomization)							
Started							
Completed							
Not Completed							
Reason Not Completed							
Stage 2 Intervention (Weeks 12-24)							
Started							
Completed							
Not Completed							

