# Appendix 3 Table 2: Clinical Trials Adverse Event Reporting Table Serious Adverse Events

Population: All Participants Randomized to Stage 1 (N=805); Including All Participants Randomized to Stage 2 (N=683)

System Organ Class	Preferred Term	Stage 1 ACT (N=xx)		Stage 1 Duloxetine (N=xx)		Stage 1 EBEM (N=xx)		Stage 1 ESC (N=xx)	
		Affected / at Risk (%)	# Events	Affected / at Risk (%)	# Events	Affected / at Risk (%)	# Events	Affected / at Risk (%)	# Events
	Total	x/N (x.x%)	у	x/N (x.x%)	У	x/N (x.x%)	у	x/N (x.x%)	
System Organ	Preferred Term A1	x/N (x.x%)	У	x/N (x.x%)	У	x/N (x.x%)	у	x/N (x.x%)	у
Class A System Organ	Preferred Term A2	x/N (x.x%)	У	x/N (x.x%)	У	x/N (x.x%)	у	x/N (x.x%)	у
lass A		D . ( 2()				(2) ( 2()			
ystem Irgan lass B	Preferred Term B1	x/N (x.x%)	У	x/N (x.x%)	У	x/N (x.x%)	У	x/N (x.x%)	У
ystem rgan lass B	Preferred Term B2	x/N (x.x%)	У	x/N (x.x%)	У	x/N (x.x%)	у	x/N (x.x%)	У

Serio	us Advers	e Events							
System Organ Class	Preferred Term	Stage 2 AC	T (N=xx)	Stage 2 Dulox	cetine (N=xx)	Stage 2 EB	EM (N=xx)	Stage 2 ESC (N=xx)	
5.0.00		Affected / at Risk (%)	# Events	Affected / at Risk (%)	# Events	Affected / at Risk (%)	# Events	Affected / at Risk (%)	# Events
	Total	x/N (x.x%)	у	x/N (x.x%)	У	x/N (x.x%)	У	x/N (x.x%)	
-	Preferred Term A1	x/N (x.x%)	у	x/N (x.x%)	У	x/N (x.x%)	У	x/N (x.x%)	У
System	Preferred Term A2	x/N (x.x%)	У	x/N (x.x%)	У	x/N (x.x%)	У	x/N (x.x%)	у
-	Preferred Term B1	x/N (x.x%)	У	x/N (x.x%)	У	x/N (x.x%)	У	x/N (x.x%)	У
_	Preferred Term B2	x/N (x.x%)	У	x/N (x.x%)	У	x/N (x.x%)	у	x/N (x.x%)	У

Serio	Serious Adverse Events											
- 3	Preferred Term	Stage 2 ACT and Duloxetine (N=xx)		Stage 2 ACT and EBEM (N=xx)		Stage 2 ACT and ESC (N=xx)		Stage 2 Duloxetine and EBEM (N=xx)				
		Affected / at Risk (%)	# Events	Affected / at Risk (%)	# Events	Affected / at Risk (%)	# Events	Affected / at Risk (%)	# Events			

	Total	x/N (x.x%)	V	x/N (x.x%)	у	x/N (x.x%)	у	x/N (x.x%)	
						1			
System	Preferred	x/N (x.x%)	у						
_	Term A1								
Class A									
System	Preferred	x/N (x.x%)	у						
Organ	Term A2								
Class A									
System	Preferred	x/N (x.x%)	у						
Organ	Term B1								
Class B									
				0.4				200	
-	Preferred	x/N (x.x%)	У						
_	Term B2								
Class B									

System Organ Class	Preferred Term	Stage 2 Dulo ESC(N		Stage 2 EBEM and ESC (N=xx)		
		Affected / at Risk (%)	# Events	Affected / at Risk (%)	# Events	
	Total	x/N (x.x%)	у	x/N (x.x%)	у	

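### The adverse event tables give no harm figure by Stage 1 randomised arm over the 24 weeks for which efficacy is reported by that arm

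*SAP*

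**What the plan says.** **Efficacy.** The second aim in SAP Objectives is "Estimate 24-week least squares means for study outcomes by Stage 1 treatment assignment". SAP Analysis Methods models Week 24 outcomes "by the Stage 1 treatment assignment for all continuous outcomes". SAP Analysis Populations states: "The population used for statistical analysis consists of the 805 randomized participants to a Stage 1 treatment".

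**Harms.** Appendix 3 Tables 1 (deaths), 2 (serious events) and 3 (other events) share the population line "Population: All Participants Randomized to Stage 1 (N=805); Including All Participants Randomized to Stage 2 (N=683" and the same 14 columns:
- four for the Stage 1 treatments;
- four for a single Stage 2 treatment;
- six for Stage 2 pairs, such as "Stage 2 Duloxetine and EBEM (N=xx".

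No column names a Stage 1 arm together with Stage 2, and none covers all participants. The row labelled Total adds over event terms within a column, not over arms. Appendix 3 gives no event window for any column.

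**Stage dates.** The SAP flow table heads its first block "Stage 1 Intervention (Weeks 0-12" and dates the Stage 2 block Weeks 12-24. It keeps the Stage 1 arm visible through Stage 2, in 43 groups.

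**Stage 2 assignment.** Under Protocol 7.1, "individuals assigned to ESC at the first randomization will maintain ESC if PGIC is 1-2 and PEG<4 else they will augment ESC" with a randomly chosen treatment. In the other arms, participants with PGIC 1-2 maintain or augment depending on PEG, those with PGIC 3-4 are to "be randomized to augmentation or switching to a new treatment (PGIC=3-4", and those with PGIC 5-7 switch.

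**Recording and safety analysis.** Protocol 12.3.4 records events from consent to 4 weeks after last treatment. Protocol 13.4.4 limits safety analysis to descriptive summaries and listings.

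**The concern.** The Week 24 mean for a Stage 1 arm includes the effect of whatever was added or substituted at Week 12. The harms of that later treatment are tabulated in Stage 2 columns shared with starters from other arms. A reader who sets benefit beside harm therefore has a 24-week randomised comparison for benefit. For harm there is a Stage 1 comparison, followed by pooled groups formed partly by response.

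The pooled columns do not stand in for a randomised comparison. Stage 2 treatment is randomised only within Stage 1 arm and response class, and the best responders are assigned to maintain without re-randomisation. The column for duloxetine alone in Stage 2, for example, combines duloxetine starters who did well and stayed on it with ACT and EBEM starters who responded less well and are taking it for the first time.

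At stake is whether the report can show, for the groups the trial randomised, how many people had a serious or other event over the period of the efficacy result.

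**Working it through.** **Inputs.** Stage 1 arm sizes from the SAP baseline table: ACT 203, duloxetine 198, EBEM 199, ESC 205. Stage 2 number from Appendix 3: 683. Permitted paths from Protocol Table 10.1, plus maintenance.

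**1. The plan's own total.** 203 + 198 + 199 + 205 = 805, as stated.

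**2. Outside Stage 2.** 805 - 683 = 122 participants (122/805 = 15.2%). Appendix 3 does not say where their later events are counted. The flow table places participants not assessed at the end of Stage 1 in the single-treatment (Alone) groups. The line speaks of participants randomised to Stage 2, so it is also not explicit whether maintainers are among the 683; the single-treatment columns suggest that they are.

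**3. Paths and columns.** ACT, duloxetine and EBEM starters each have 1 maintain + 3 augment + 3 switch = 7 paths. ESC starters have 1 maintain + 3 augment = 4. Total 7 + 7 + 7 + 4 = 25 paths, mapped to 10 columns:

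| Stage 2 column | Stage 1 arms pooled |
|---|---|
| ACT alone | ACT, duloxetine, EBEM |
| Duloxetine alone | ACT, duloxetine, EBEM |
| EBEM alone | ACT, duloxetine, EBEM |
| ESC alone | all four |
| each of six pairs | the two arms named |

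The check on the count is 3 + 3 + 3 + 4 + (6 x 2) = 25.

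**4. Can an arm's Stage 2 total be rebuilt?** Only if the arm fills every column it appears in. Each column holds at least two arms, so it cannot be done for any of the four. A matrix-rank check gave the same answer.

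**5. Can distinct participants be counted?** The column Ns add to 805 + 683 = 1,488 for 805 people. In Tables 2 and 3 someone affected in both stages is counted in two columns. As an illustration, assume 3% have a serious event in each stage: 805 x 0.03 = 24.2 and 683 x 0.03 = 20.5, together 44.6 entries. The distinct number could lie anywhere from about 24 (full overlap) to about 45 (none). In Table 1 a person dies once, so total deaths can be summed if every death is placed in some column. Deaths after Week 12 still cannot be assigned to a Stage 1 arm.

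**6. Illustration of direction only.** None of these rates is in the documents. Assume 3% incidence per stage, or s in the stage when duloxetine is started. Take f = 683/805 = 0.848 for every arm. Assume 60-90% of ESC starters in Stage 2 do not maintain and one third of those get duloxetine, so the share starting it is d = 0.20-0.30. Then:

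24-week incidence = 1 - (1 - p1)(1 - f x p2), with p2 = d x s + (1 - d) x 0.03 for ESC.

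With s = 0.20:
- ESC: p1 = 0.03 and p2 = 0.064-0.081, giving 8.3-9.7%, against 3.0% in Stage 1.
- Duloxetine: p1 = 0.20 and p2 = 0.03, giving 22.0%.
- Difference: 12.4-13.8 points, against 17 in Stage 1.

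With s = 0.10 the difference is 5.1-5.7 against 7 points; with s = 0.30 it is 19.6-21.9 against 27. The one-third share ignores contraindications to duloxetine and is probably high.

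**The case against.** The case for leaving the tables alone has weight. The SAP plans no hypothesis tests and says that the least squares mean is not the trial's primary estimand. The protocol promises only descriptive safety summaries and listings. Attributing an event to the treatment being received is a sensible descriptive choice, and it is the reason to keep the stage columns. It does not supply the figure that belongs beside the Week 24 arm means.

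A reader might infer more than the documents support:
- *That the harms of treatments added to ESC are hidden.* Under the protocol ESC starters do not switch, so every Stage 2 event in an ESC starter falls in a column that names ESC. The difficulty is that other starters share that column. (The flow table's descriptions of the ESC-plus groups say ESC was discontinued, contrary to their own titles and to the protocol; this reading follows the protocol.)
- *That all three tables double count.* Table 1 does not.
- *That the Stage 1 columns certainly end at Week 12.* This is inferred from the column labels and the flow table headings. A reading in which they run through all follow-up is less natural, but the appendix does not exclude it.
- *That randomisation is abandoned in Stage 2.* Most Stage 2 treatments are randomised within Stage 1 arm and response class. Pooling loses that structure.
- *That augment and switch columns are needed for PGIC 3-4.* This SAP reports no matching efficacy result, so alignment does not require them.

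**Conclusion.** The point holds as a reporting gap. Benefit is summarised for four randomised arms at Week 24. On the natural reading of the stage labels, no planned table gives harms for those arms over the same period. Because the 25 paths collapse into ten mixed columns, the missing figures cannot be rebuilt from the tables. For serious and other events the number of distinct people affected, overall or by arm, is also lost.

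The structural result rests on the column layout and the protocol's permitted paths. The statement about the period rests on the inferred windows. The size of any distortion is unknown: the incidence figures above show direction under assumed rates and are not a finding. The trial data would support the comparison; only the planned tables do not. No estimate, confidence interval, sample size or element of conduct is affected.

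**What to change.** In SAP Appendix 3:
1. Keep the existing 14 columns as descriptive summaries by current treatment, and note that the pooled Stage 2 columns are not randomised comparison groups.
2. State the event window of each column, including where later events in the 122 participants not randomised to Stage 2 are counted.
3. Add four columns by Stage 1 randomised arm (N = 203, 198, 199, 205) and one total (N = 805). Count each participant once, from first randomisation through Week 24, and name these as the columns to read beside the Week 24 means.
4. Show events in the rest of the recording period (to 4 weeks after last treatment) separately, or include them under a clear label, so that the Week 24 match is kept.

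The cost is SAP wording and table programming. The flow table already links Stage 1 arm to Stage 2, so no new data are needed. The downside is wider tables and a less favourable cumulative harm figure for some arms.

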# Appendix 3 Table 2: Clinical Trials Adverse Event Reporting Table Serious Adverse Events

Population: All Participants Randomized to Stage 1 (N=805); Including All Participants Randomized to Stage 2 (N=683)

System Organ Class	Preferred Term	Stage 1 ACT (N=xx)		Stage 1 Duloxetine (N=xx)		Stage 1 EBEM (N=xx)		Stage 1 ESC (N=xx)	
		Affected / at Risk (%)	# Events	Affected / at Risk (%)	# Events	Affected / at Risk (%)	# Events	Affected / at Risk (%)	# Events
	Total	x/N (x.x%)	у	x/N (x.x%)	У	x/N (x.x%)	у	x/N (x.x%)	
System Organ	Preferred Term A1	x/N (x.x%)	У	x/N (x.x%)	У	x/N (x.x%)	у	x/N (x.x%)	у
Class A System Organ	Preferred Term A2	x/N (x.x%)	У	x/N (x.x%)	У	x/N (x.x%)	у	x/N (x.x%)	у
lass A		D . ( 2()				(2) ( 2()			
ystem Irgan lass B	Preferred Term B1	x/N (x.x%)	У	x/N (x.x%)	У	x/N (x.x%)	У	x/N (x.x%)	У
ystem rgan lass B	Preferred Term B2	x/N (x.x%)	У	x/N (x.x%)	У	x/N (x.x%)	у	x/N (x.x%)	У

Serio	us Advers	e Events							
System Organ Class	Preferred Term	Stage 2 AC	T (N=xx)	Stage 2 Dulox	cetine (N=xx)	Stage 2 EB	EM (N=xx)	Stage 2 ESC (N=xx)	
5.0.00		Affected / at Risk (%)	# Events	Affected / at Risk (%)	# Events	Affected / at Risk (%)	# Events	Affected / at Risk (%)	# Events
	Total	x/N (x.x%)	у	x/N (x.x%)	У	x/N (x.x%)	У	x/N (x.x%)	
-	Preferred Term A1	x/N (x.x%)	у	x/N (x.x%)	У	x/N (x.x%)	У	x/N (x.x%)	У
System	Preferred Term A2	x/N (x.x%)	У	x/N (x.x%)	У	x/N (x.x%)	У	x/N (x.x%)	у
-	Preferred Term B1	x/N (x.x%)	У	x/N (x.x%)	У	x/N (x.x%)	У	x/N (x.x%)	У
_	Preferred Term B2	x/N (x.x%)	У	x/N (x.x%)	У	x/N (x.x%)	у	x/N (x.x%)	У

Serio	Serious Adverse Events											
- 3	Preferred Term	Stage 2 ACT and Duloxetine (N=xx)		Stage 2 ACT and EBEM (N=xx)		Stage 2 ACT and ESC (N=xx)		Stage 2 Duloxetine and EBEM (N=xx)				
		Affected / at Risk (%)	# Events	Affected / at Risk (%)	# Events	Affected / at Risk (%)	# Events	Affected / at Risk (%)	# Events			

	Total	x/N (x.x%)	V	x/N (x.x%)	у	x/N (x.x%)	у	x/N (x.x%)	
						1			
System	Preferred	x/N (x.x%)	у						
_	Term A1								
Class A									
System	Preferred	x/N (x.x%)	у						
Organ	Term A2								
Class A									
System	Preferred	x/N (x.x%)	у						
Organ	Term B1								
Class B									
				0.4				200	
-	Preferred	x/N (x.x%)	У						
_	Term B2								
Class B									

System Organ Class	Preferred Term	Stage 2 Dulo ESC(N		Stage 2 EBEM and ESC (N=xx)		
		Affected / at Risk (%)	# Events	Affected / at Risk (%)	# Events	
	Total	x/N (x.x%)	у	x/N (x.x%)	у	
System Organ Class A	Preferred Term A1	x/N (x.x%)	У	x/N (x.x%)	у	
System Organ Class A	Preferred Term A2	x/N (x.x%)	у	x/N (x.x%)	у	
System Organ Class B	Preferred Term B1	x/N (x.x%)	У	x/N (x.x%)	У	
System Organ Class B	Preferred Term B2	x/N (x.x%)	У	x/N (x.x%)	у	

# Appendix 3 Table 3: Clinical Trials Adverse Event Reporting Table Other (Not Including Serious) Adverse Events Over a Threshold of 5%

Population: All Participants Randomized to Stage 1 (N=805); Including All Participants Randomized to Stage 2 (N=683)

	/ Threshold ing Other Events	5%							
System Organ Class	Preferred Term	Stage 1 ACT (N=xx)		Stage 1 Duloxetine (N=xx)		Stage 1 EBEM (N=xx)		Stage 1 ESC (N=xx)	
		Affected / at Risk (%)	# Events	Affected / at Risk (%)	# Events	Affected / at Risk (%)	# Events	Affected / at Risk (%)	# Events
	Total	x/N (x.x%)	у	x/N (x.x%)	У	x/N (x.x%)	У	x/N (x.x%)	
System Organ Class A	Preferred Term A1	x/N (x.x%)	у	x/N (x.x%)	у	x/N (x.x%)	У	x/N (x.x%)	У
System Organ Class A	Preferred Term A2	x/N (x.x%)	У	x/N (x.x%)	у	x/N (x.x%)	У	x/N (x.x%)	У
System Organ Class B	Preferred Term B1	x/N (x.x%)	У	x/N (x.x%)	У	x/N (x.x%)	У	x/N (x.x%)	У
System Organ Class B	Preferred Term B2	x/N (x.x%)	у	x/N (x.x%)	у	x/N (x.x%)	У	x/N (x.x%)	У

Othe	r (Not Inclu	ıding Serious)	Adverse E	vents					
Frequent Threshol Reportin Adverse	ld for g Other	5%							
	Preferred Term	Stage 2 ACT (N=xx)		Stage 2 Duloxetine (N=xx)		Stage 2 EBEM (N=xx)		Stage 2 ESC (N=xx)	
		Affected / at Risk (%)	# Events	Affected / at Risk (%)	# Events	Affected / at Risk (%)	# Events	Affected / at Risk (%)	# Events
	Total	x/N (x.x%)	у	x/N (x.x%)	у	x/N (x.x%)	У	x/N (x.x%)	
System Organ Class A	Preferred Term A1	x/N (x.x%)	У	x/N (x.x%)	у	x/N (x.x%)	У	x/N (x.x%)	у
System	Preferred Term A2	x/N (x.x%)	у	x/N (x.x%)	у	x/N (x.x%)	У	x/N (x.x%)	У
System Organ Class B	Preferred Term B1	x/N (x.x%)	у	x/N (x.x%)	У	x/N (x.x%)	у	x/N (x.x%)	У
System Organ Class B	Preferred Term B2	x/N (x.x%)	у	x/N (x.x%)	У	x/N (x.x%)	у	x/N (x.x%)	У

Othe	r (Not Inclu	ıding Serious)	Adverse E	vents					
Frequent Threshol Reportin Adverse	ld for g Other	5%							
	Preferred Term	Stage 2 ACT and Duloxetine (N=xx)		Stage 2 ACT and EBEM (N=xx)		Stage 2 ACT and ESC (N=xx)		Stage 2 Duloxetine and EBEM (N=xx)	
		Affected / at Risk (%)	# Events	Affected / at Risk (%)	# Events	Affected / at Risk (%)	# Events	Affected / at Risk (%)	# Events
	Total	x/N (x.x%)	у	x/N (x.x%)	У	x/N (x.x%)	У	x/N (x.x%)	
_	Preferred Term A1	x/N (x.x%)	У	x/N (x.x%)	У	x/N (x.x%)	У	x/N (x.x%)	у
System	Preferred Term A2	x/N (x.x%)	У	x/N (x.x%)	у	x/N (x.x%)	У	x/N (x.x%)	У
	Preferred Term B1	x/N (x.x%)	У	x/N (x.x%)	У	x/N (x.x%)	У	x/N (x.x%)	У
-	Preferred Term B2	x/N (x.x%)	у	x/N (x.x%)	У	x/N (x.x%)	у	x/N (x.x%)	У

Othe	r (Not Incl	uding Serious	) Adverse E	vents			
Frequent Threshol Reportin Adverse	d for g Other Events	5%					
System Organ Class	Preferred Term	Stage 2 Dulo		Stage 2 EBEM and ESC (N=xx)			
		Affected / at Risk (%)	# Events	Affected / at Risk (%)	# Events		
	Total	x/N (x.x%)	у	x/N (x.x%)	У		
System Organ Class A	Preferred Term A1	x/N (x.x%)	У	x/N (x.x%)	У		
System Organ Class A	Preferred Term A2	x/N (x.x%)	у	x/N (x.x%)	у		
System Organ Class B	Preferred Term B1	x/N (x.x%)	у	x/N (x.x%)	у		
System Organ Class B	Preferred Term B2	x/N (x.x%)	У	x/N (x.x%)	у
